5.4. Risks of Study Procedures

The only study-related procedures to be performed will be venipunctures for blood drawing and collection of nasal swabs. Venipuncture carries the risk of local pain, redness or swelling. Collection of nasal swabs may be associated with transient mild discomfort or epistaxis

5.5. Potential Benefits

Participants might benefit from participating in this trial if the IC14 antibody treatment improves the time to recovery from COVID-19 illness and/or if IC14 antibody treatment improves the number of days-alive-and-free of higher-level respiratory support in an intensive care unit, and they are randomized to the active treatment group. If the IC14 antibody treatment does not have benefits, then the participants will have no direct benefits from participating in this trial. Participants who participate in this trial will be helping other people in the future because this trial will help to determine what therapeutic agents in combination with remdesivir do or do not work for the treatment of COVID-19 illness.

6. Investigational Agent Intervention

6.1. Investigational Agent

6.1.1. Investigational Agent

The study drug/investigational agent, IC14, will be supplied to DAIT/NIAID by Implicit Bioscience Ltd. (Seattle, WA, USA). IC14 is a recombinant chimeric (murine/human) mAb against human CD14 in which the murine variable regions have been combined with IgG4 constant regions. The mAb binds surface and soluble human CD14 proteins with high affinity. IC14 is secreted from Chinese hamster ovary cells as an L₂H₂γ₄ immunoglobulin. IC14 bulk product is manufactured by AGC Biologics, Inc. (Bothell, WA, USA) under Good Manufacturing Practice guidelines.

IC14 drug product is manufactured by Althea Technologies, Inc. (now Ajinomoto Bio-Pharma Services, San Diego, CA, USA) under Good Manufacturing Practice guidelines.

6.1.1.1. Formulation, Packaging, Labeling and Shipping

The investigational drug product will be supplied as a sterile solution at a concentration of 5 mg/mL for intravenous administration totaling 125 mg in a volume of 25 mL in a 30-mL single-use glass vial. More than one vial may be required to prepare each dose.

IC14 drug product (Lot No. 1-FIN-0779) will be shipped from Implicit Bioscience's GMP storage facility maintained by Caligor Coghlan Pharma Services (Bastrop, TX) to the DAIT/ NIAID Distributor, Eminent Corporation (Frederick MD), who will add a label containing the study sponsor name and study ID. Glass vials (30 mL volume) of IC14 containing 125 mg of IC14 at

25 mg/mL are stored in tamper-resistant cardboard cartons that contain 10 vials per carton and are secured by a foam insert. IC14 must be stored and transported at 2-8°C (36-46 F) in an upright position and protected from light. The temperature of all drug shipments is monitored and recorded by TempTale devices added to pre-conditioned and qualified shipping containers.

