Study Duration	Approximately 6 months recruitment, 4 days treatment, 56 days follow up off treatment (8 months from first participant first visit to last participant, last visit)
Treatment Description	
Intervention Arm: IC14 4 mg/kg intravenously (IV) on day 1, followed by IC14 2 mg/kg/day IV on days 2-4 (total 4 consecutive days). Placebo Arm: 0.9% w/v NaCl in a matching bag and volume administered IV daily on day 1-4 (total 4 consecutive days). All randomized participants will receive remdesivir 200 mg IV on day 1 followed by 100 mg IV/day on days 2-5 (total 5 consecutive days)

Inclusion Criteria	
Patients included in the study must meet all the following criteria:
 
 1. Patient or legally authorized representative able to provide informed consent 2. Age ≥ 18 years 3. Presence of SARS-CoV-2 infection documented by positive RT-PCR testing within 7 days of screening 4. Radiologic findings compatible with diagnosis of SARS-CoV-2 pulmonary infection with no alternative explanation for radiologic findings. 5. Hypoxemia as defined by any of the following: 
 a. $\text{SpO}_2 \leq 94\%$ on room air, or b. Requirement for $\geq 2\text{L}/\text{m}$ O_2 per standard nasal cannula to maintain $\text{SpO}_2 >= 94\%$, but not requiring high-flow nasal cannula (defined as $\geq 30 \text{ L}/\text{m}$) 6. Women of childbearing potential must have a negative pregnancy test and be willing to use birth control for the duration of the study.

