6.1.1.2. Dosage, Preparation, and Administration

The dosage regimen to be studied has been used safely in prior investigations of IC14 as a treatment for community-acquired pneumonia, severe sepsis and ARDS (Axtelle et al 2003; Reinhart et al 2004). In normal volunteers, a single intravenous dose of 4 mg/kg produced a Cmax = 72.85 mcg/mL with a T_{1/2} = 15.79 hr. In participants with community-acquired pneumonia and sepsis treated with the proposed dosing regimen of 4 mg/kg on Day 1 followed by 2 mg/kg on Days 2, 3 4, the Cmax = 52.7 mcg/mL with a T1/2 = 23.6 hr. (Axtelle et al. 2003).

Participants will receive a dose of 4 mg/kg in a solution of 250 mL 0.9% w/v NaCl over 2 hours on Study Day 1, followed by 2 mg/kg in a solution of 250 mL 0.9% w/v NaCl over 2 hours once daily on Study Days 2-4. Premedication with antihistamines or corticosteroids is not necessary based on treatment of 168 normal volunteers and participants with infections (Section 5.1). Study drug will be administered as a single dose daily for four consecutive days at approximately 24-hr intervals. The dose of study drug will be calculated based on body weight of the participant. The maximum dose administered will be that for a 125-kg participant (i.e., if a participant weighs >125 kg, the dose of study drug will be calculated based on a weight of 125 kg – i.e. maximum dose is 500mg on study day 1 and 250 mg on study days 2-4). Preparation of the infusion bag may occur up to 12 hours before administration. Once prepared, the infusion bag must be kept refrigerated at 2-8°C until the time of administration. Placebo will consist of an identical-appearing infusion of 250 mL 0.9% w/v NaCl over 2 hours once daily.

Participants will not be pretreated with antihistamines or steroids prior to infusion of study drug because of the rarity of infusion reactions in clinical studies with IC14 (e.g. one infusion reaction in 168 participants treated to date),, and the likelihood that many participants will be receiving corticosteroids as part of standard of care. However, if three or more infusion reactions occur during the study, consideration will be given to adding pretreatment prior to infusion of the study drug in subsequent participants.

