7.1. Concomitant Medications

7.1.1. Protocol-mandated medications

All participants in this study will receive remdesivir (antiviral) according to current approved dosing for COVID-19 illness. Remdesivir will be provided by Gilead Sciences, Inc., for the study and administered intravenously for 5 days beginning with a 200 mg loading dose on Day 1, followed by 100 mg/day on Days 2-5 (Beigel et al. 2020). Study participants may receive up to 10 doses of remdesivir if they have received up to 4 doses (including the loading dose) of this agent for the treatment of COVID-19 prior to enrolling in the study. If already on remdesivir prior to randomization, a second loading dose should not be administered.

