8.3.2. Study Day 1 – Treatment and Post-Treatment

- Administer study drug over 2 hours. The participant should be monitored during infusion and for 1 hour following infusion. Document any interruption of study drug infusion during administration.
- Administer remdesivir 200 mg IV loading dose.
- Collect blood for study labs
 - Process and freeze (-80°C) serum for IC14 PK measurement approximately 1 hour after dosing is completed (to be collected on 40 participants)
- Record vital signs (blood pressure, respiratory rate, heart rate, and temperature) approximately 30 and 60 min after completion of study drug.
- Record variables for Sequential Organ Failure Assessment score (SOFA; Appendix A)
- Determine and record Eight-Point Ordinal Scale performed twice daily as close as possible to 8:00 a.m. and 8:00 p.m. (Appendix C)
- After completion of study infusion, complete the following evaluations in Section 8.3.3..

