3. A full ocular examination should be scheduled when the participant is clinically stable, free of COVID-19 symptoms, beyond the quarantine period, and able to comply with the exam (typically between Day 28 and before Day 60)..

4. Draw or record labs per section 8.3 at baseline and Days 2, 3, 4, 7, 14, 21, 28 if hospitalized and if not collected as part of clinical care (values closest to 8:00 am on study day. * Record Daily and Days 3 and 5 clinical lab values only if drawn as part of clinical care.

5. Whole blood samples to be drawn at selected sites on a total of 30 participants enrolled.

6. Serum PK on Days 2-4 should be drawn before study drug infusion on 40 participants.

7. Additional unscheduled sampling of anti-drug antibodies should be performed if participant has a suspected immunologically related AE.

8. Collect plasma for prognostic biomarkers.

9. Study drug will be given as a 120-min IV infusion as a single dose once daily for four consecutive days (at 24-hr intervals).

10. Remdesivir will be given as loading dose 200 mg IV on day 1 then 100 mg IV on day 2-5

11. To be assessed through examination of daily progress notes and through communication with bedside nurse and, if possible, participant

12. If still hospitalized.

13. Preferred that this visit is in person to obtain safety laboratory tests and clinical outcome data. However, if participant is unable to return to the study site clinic the visit may be conducted by phone or virtually and the chest radiograph and labs scheduled as soon as possible. If not still hospitalized and not seen in clinic, record the most recent lab values.

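### Section 6.1.1.1 gives two concentrations, 5 and 25 mg/mL, for the same 125 mg IC14 vial; separately, three places order a Day 1 remdesivir loading dose without the exception in 7.1.1

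*Combined protocol and SAP*

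**What the plan says.** **IC14 vial.** Section 6.1.1.1 states the concentration twice. The first paragraph describes a "sterile solution at a concentration of 5 mg/mL for intravenous administration totaling 125 mg in a volume of 25 mL", in a 30-mL vial. The second paragraph, on labelling and shipping, reads "Glass vials (30 mL volume) of IC14 containing 125 mg of IC14 at" and continues "25 mg/mL are stored in tamper-resistant cardboard cartons that contain 10 vials per carton". One lot is named, no second presentation is described, and no other section gives a vial concentration. Section 6.1.1.2 sets the dose by weight, "The dose of study drug will be calculated based on body weight of the participant", at 4 mg/kg on Day 1 and 2 mg/kg on Days 2-4, with the weight capped at 125 kg (500 mg and 250 mg).

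**Remdesivir.** Three places give the Day 1 dose with no exception:

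- Synopsis, Treatment Description: "All randomized participants will receive remdesivir 200 mg IV on day 1 followed by 100 mg IV/day on days 2-5".
- Section 8.3.2, Study Day 1: "Administer remdesivir 200 mg IV loading dose".
- Table 3, footnote 10: "Remdesivir will be given as loading dose 200 mg IV on day 1 then 100 mg IV on day 2-5".

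Section 7.1.1 gives the same general schedule and then adds "If already on remdesivir prior to randomization, a second loading dose should not be administered". Exclusion 15 (synopsis and Section 4.3) bars only patients with five or more earlier doses, and 7.1.1 provides expressly for up to four.

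**The concern.** The two vial descriptions agree on content (125 mg) and vial size (30 mL) but differ five-fold in concentration. Whoever prepares a weight-based dose will usually have to draw part of a vial by volume, and that step needs the concentration. If the wrong figure is used, the participant receives a dose other than the stated mg/kg.

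The remdesivir point is a conflict between instructions that a site acts on. For a participant who arrives with one to four earlier doses, following the Day 1 procedure as written departs from 7.1.1, and following 7.1.1 departs from the Day 1 procedure, the schedule footnote and the synopsis. Section 16.1 counts any departure from study procedures as a deviation, so either course can be recorded as one.

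**Working it through.** **Inputs.** Vial content, fill volume and both concentrations: Section 6.1.1.1. Dose per kg and the 125-kg cap: Section 6.1.1.2. Body weights of 80 kg and 50-125 kg are assumptions used only to size the discrepancy.

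**Step 1: the protocol's own figure.** Concentration = content / volume = 125 mg / 25 mL = 5 mg/mL. The first statement agrees with itself.

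**Step 2: the second figure.** Volume = content / concentration = 125 mg / 25 mg/mL = 5 mL. Conversely, 25 mL at 25 mg/mL would hold 625 mg. Neither fits a vial of 125 mg in 25 mL. The ratio is 25 / 5 = 5.

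**Step 3: does the concentration matter for preparation?** Vials needed = dose / 125 mg, which does not involve the concentration. The dose is a whole number of vials (k) only at these weights:

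- Day 1: 125k / 4 = 31.25, 62.5, 93.75 kg, and 125 kg or more.
- Days 2-4: 125k / 2 = 62.5 kg, and 125 kg or more.

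At any other weight a part vial must be drawn.

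**Step 4: volumes for an assumed 80-kg participant.**

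| Day | Dose | Vials | mL at 5 mg/mL | mL at 25 mg/mL |
|---|---|---|---|---|
| 1 | 4 x 80 = 320 mg | 2.56 | 64 | 12.8 |
| 2-4 | 2 x 80 = 160 mg | 1.28 | 32 | 6.4 |

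**Step 5: possible dose error at 80 kg.** Suppose whole vials are counted by content and only the part vial is drawn with the wrong concentration.

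- Day 1 needs 2 vials + 70 mg, and 70 mg is 14 mL (at 5 mg/mL) or 2.8 mL (at 25 mg/mL).
  - Vial truly 5 mg/mL, 2.8 mL drawn: 250 + 2.8 x 5 = 264 mg; 264 / 80 = 3.3 mg/kg.
  - Vial truly 25 mg/mL, 14 mL sought: the 5 mL fill is emptied, 250 + 125 = 375 mg; 375 / 80 = 4.69 mg/kg.
- Days 2-4 need 1 vial + 35 mg, and 35 mg is 7 mL or 1.4 mL.
  - Low: 125 + 1.4 x 5 = 132 mg; 132 / 80 = 1.65 mg/kg.
  - High: 125 + 125 = 250 mg; 250 / 80 = 3.125 mg/kg.

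**Step 6: other weights.** The same calculation at each whole kilogram from 50 to 125 gives these extremes:

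- Day 1: 2.41 mg/kg at 62 kg (125 + 123/5 = 149.6 mg) to 5.43 mg/kg at 69 kg (250 + 125 = 375 mg).
- Days 2-4: 0.40 mg/kg at 50 to 62 kg, where the whole dose is a part vial (at 50 kg, 100/5 = 20 mg), to 3.33 mg/kg at 75 kg (125 + 125 = 250 mg).

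If vial content were ignored altogether, the Day 1 error at 80 kg would be five-fold: 12.8 mL x 5 = 64 mg (0.8 mg/kg), or 64 mL x 25 = 1600 mg (20 mg/kg).

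**Step 7: remdesivir.** No arithmetic applies. The three unconditional instructions and the restriction in 7.1.1 diverge only for participants already on remdesivir. Exclusion 15 leaves patients with one to four earlier doses eligible, so the divergence reaches people who can be enrolled. None of the three places refers to 7.1.1, and no rule says which section prevails.

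**The case against.** On the vial: the 25 mg/mL figure sits in a shipping sentence, not in the preparation section, and gives no fill volume. The formulation sentence is complete and self-consistent. The figure follows a line break in the text as read from the PDF, so the page itself should be checked; a slip for the 25 mL fill volume is possible, though the documents do not say so. The mg/kg ranges need a preparer who counts whole vials by content and then ignores content for the last one. The high side also needs that person to seek more volume than the vial holds and not notice. The 20 mg/kg case would consume 1600 / 125 = 12.8 vials and exceeds the 500 mg Day 1 maximum.

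All of that limits the weight to put on the dose ranges: they are bounds under stated assumptions, and the five-fold case is remote. It does not remove the contradiction. Even a misprint in a drug concentration needs correcting.

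On remdesivir: 7.1.1 puts the general schedule and the exception in one paragraph, so they can be read together. A synopsis and a table footnote commonly abbreviate, and none of the three places expressly tells a site to repeat a loading dose. That is fair for the synopsis and the footnote. It is weaker for Section 8.3.2, a Day 1 procedure that breaches 7.1.1 if followed as written for a pre-treated participant.

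**Conclusion.** Both inconsistencies stand. Section 6.1.1.1 gives one product two concentrations that differ five-fold, and nothing else in the documents resolves them. The mg/kg doses, the weight cap and the 125 mg per vial are consistent throughout, so the exposure is confined to drawing by volume. Under the part-vial error, at an assumed 80 kg, the dose could run from 3.3 to 4.7 mg/kg against the stated 4, and from 1.65 to 3.1 mg/kg against the stated 2. No actual error is shown.

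The remdesivir conflict affects only participants who enter with one to four earlier doses; their share is not given. Neither point affects the sample size, power or planned analyses. The correction is still worth making because pharmacies and sites act on these statements directly.

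**What to change.** After checking the 25 mg/mL figure on the PDF page, reconcile the two statements in Section 6.1.1.1 with the product label, so that one concentration and one fill volume appear. Reconcile the synopsis, Section 8.3.2 and Table 3 footnote 10 with Section 7.1.1 for participants already on remdesivir. Which concentration and which remdesivir instruction is right is for the sponsor to settle; this review takes no position.

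The cost is a wording correction in the next amendment, with a clarification memo to pharmacies and sites until then.

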6.1.1.2. Dosage, Preparation, and Administration

The dosage regimen to be studied has been used safely in prior investigations of IC14 as a treatment for community-acquired pneumonia, severe sepsis and ARDS (Axtelle et al 2003; Reinhart et al 2004). In normal volunteers, a single intravenous dose of 4 mg/kg produced a Cmax = 72.85 mcg/mL with a T_{1/2} = 15.79 hr. In participants with community-acquired pneumonia and sepsis treated with the proposed dosing regimen of 4 mg/kg on Day 1 followed by 2 mg/kg on Days 2, 3 4, the Cmax = 52.7 mcg/mL with a T1/2 = 23.6 hr. (Axtelle et al. 2003).

Participants will receive a dose of 4 mg/kg in a solution of 250 mL 0.9% w/v NaCl over 2 hours on Study Day 1, followed by 2 mg/kg in a solution of 250 mL 0.9% w/v NaCl over 2 hours once daily on Study Days 2-4. Premedication with antihistamines or corticosteroids is not necessary based on treatment of 168 normal volunteers and participants with infections (Section 5.1). Study drug will be administered as a single dose daily for four consecutive days at approximately 24-hr intervals. The dose of study drug will be calculated based on body weight of the participant. The maximum dose administered will be that for a 125-kg participant (i.e., if a participant weighs >125 kg, the dose of study drug will be calculated based on a weight of 125 kg – i.e. maximum dose is 500mg on study day 1 and 250 mg on study days 2-4). Preparation of the infusion bag may occur up to 12 hours before administration. Once prepared, the infusion bag must be kept refrigerated at 2-8°C until the time of administration. Placebo will consist of an identical-appearing infusion of 250 mL 0.9% w/v NaCl over 2 hours once daily.

Participants will not be pretreated with antihistamines or steroids prior to infusion of study drug because of the rarity of infusion reactions in clinical studies with IC14 (e.g. one infusion reaction in 168 participants treated to date),, and the likelihood that many participants will be receiving corticosteroids as part of standard of care. However, if three or more infusion reactions occur during the study, consideration will be given to adding pretreatment prior to infusion of the study drug in subsequent participants.

The study drug or placebo should be administered via a volumetric infusion pump using standard tubing. Filtration of the study drug (IC14) is not needed prior to or during infusion. The infusion should be via a dedicated IV line or lumen of a multiple lumen catheter, preferably with no other medications, and flushed before and after with 10 mL normal saline. It should be infused over 2 hours at a rate of approximately 2 mL/min. Study drug start and stop times must be recorded in the participants' chart.

The Pharmacy will blind the study drug and the placebo for infusion using institutional standard operating procedures. All study personnel other than the study pharmacist will be blinded to study drug assignment.

Participants who improve rapidly and qualify for hospital discharge before completing all of the study drug infusions will not be held in the hospital to complete all infusions of the study drug; however they will remain in the intent-to-treat population provided that they have been randomized and have received one or more doses of the study drug.

6.1.1.3. Storage

Study drug must be refrigerated at 2-8°C. IC14 is a protein and should not be frozen, vigorously shaken, or transported via pneumatic tube delivery systems. To ensure appropriate storage conditions, refrigerator temperatures should be measured and recorded daily. The storage area should have access restricted to study personnel only.

6.2. Drug Accountability

Under Title 21 of the Code of Federal Regulations (21CFR §312.62) the investigator will maintain adequate records of the disposition of the investigational agent, including the date and quantity of the drug received, to whom the drug was dispensed (participant-by-participant accounting), and a detailed accounting of any drug accidentally or deliberately destroyed.

Records for receipt, storage, use, and disposition will be maintained by the study site. A drug-dispensing log will be kept current for each participant. This log will contain the identification of each participant and the date and quantity of drug dispensed.

All records regarding the disposition of the investigational product will be available for inspection.

At the end of the study all unused vials will be disposed of appropriately in accordance with study protocol and any institutional Standard Operating Procedures. Reconciliation of shipped, dispensed, and remaining drug will be performed. Any discrepancies noted will be investigated, resolved and documented.

6.3. Assessment of Participant Compliance with Investigational Agent

Participant compliance with the investigational agent will be monitored based on medication administration records in the participant's medical record and the study records.

6.4. Toxicity Prevention and Management

The study treatment (dose, timing, duration) should not be modified. The study medication should be stopped for suspected allergy or anaphylaxis as described below.

6.5. Premature Discontinuation of Investigational Agent

Participants may be discontinued from the study at any time for the following reasons:

- a. Suspected allergy or anaphylaxis. The study drug infusion must be discontinued, and the participant must be discontinued from further study treatment if the participant develops signs and symptoms of anaphylaxis or hypersensitivity fulfilling the following criteria (Sampson et al. 2006):

Acute onset of an illness (minutes to several hours) with involvement of the skin, mucosal tissue, or both (e.g., generalized hives, pruritus or flushing, swollen lips-tongue-uvula) and at least one of the following:

- i. Respiratory compromise (e.g., dyspnea, wheeze-bronchospasm, stridor, reduced peak expiratory flow (PEF), hypoxemia); or
- ii. Reduced BP or associated symptoms of end-organ dysfunction (e.g., hypotonia [collapse], syncope, incontinence)

Note: Collect a blood for serum tryptase measurement as soon as possible (within 60 minutes) after emergency treatment for suspected anaphylaxis. Collect another blood sample for tryptase levels between 60-120 minutes (but no later than 4 hours) after emergency treatment. If the first sample cannot be obtained within the first 60 minutes the second sample should still be obtained. In addition a baseline serum tryptase should be obtained 24 hours or more after the onset of symptoms. An elevated serum tryptase will support the diagnosis of anaphylaxis (NICE 2020). Respiratory compromise, reduced BP, or symptoms of end-organ dysfunction determined by the PI to be related to the underlying SARS-CoV-2 infection should not be considered as one of the clinical criteria for a severe allergic reaction listed above. The Site Principal Investigator should contact the VCC Medical Monitor to determine whether to discontinue study treatment for a given participant not meeting these criteria but for whom there is a clinical suspicion of a significant allergic reaction or possible anaphylaxis.

- b. Eye symptoms. If a participant develops eye symptoms such as decreased visual acuity, significant redness (above baseline), pain, or light sensitivity, they should be discontinued from study drug and scheduled for a full ophthalmic examination with slit-lamp examination as soon as feasible.
- c. New infections. If a participant develops a proven or suspected new infection during the 4 days of study drug treatment, the study drug should be discontinued, and the patient should be treated by participant's primary physicians as clinically appropriate.
- d. Other safety concerns. The Site Principal Investigator is authorized to discontinue the study drug at any time if it is in the best interest of the safety of the participant. Treatment may also be discontinued at any time at the request of the study participant.
- e. Investigator or treating physician choice. Study therapy may also be prematurely discontinued if the investigator believes that the study treatment is no longer in the best interests of the participant.
- f. Patient choice. In addition, participants who are enrolled in this study may choose to terminate their participation in the study at any time.

